qualifies as PHI. All data received at the data coordinating center (Mount Sinai) will be entered into a computerized database and stored in encrypted files on a mainframe server that is backed up nightly by the Mount Sinai Hospital IT Department.

Confidentiality during adverse event reporting. Adverse event reports and annual summaries will not include subject-identifiable material. Each will include the coded identification number only.

7. Economic Impact on Subjects:

No cost, besides transportation costs associated with in-person study visits, are expected.

8. Payments/Reimbursements to Subjects:

Study participants may receive up to \$310 for participating in the study. Study participants will receive \$50 via cash or money order after the completion of the baseline interview. An additional \$20 will be given to the participants after they return the electronic monitoring device for the medication and the electronic peak flow meter. Participants will receive \$40 in cash/money order after the completion of each follow-up interview (6 months and 12 months). An additional \$20 will be given to the participants after they return the electronic monitoring device for the medication and the electronic peak flow meter after each follow up interview. In addition, if participants participate in the pilot study, they will receive \$20 in cash/money order after the completion of the first interview (12.5 month visit) and \$30 for each of the follow-up interviews (14 months and 15 months). An additional \$20 will be given to the participants after they return the electronic monitoring device for the medication and the electronic peak flow meter after each pilot interview. Payment for each interview and device return is not contingent upon the completion of the entire study. Study participants will be paid in cash/money order for returning their devices at the next visit unless otherwise requested. If patients receive a device at the 15-month pilot visit and return it (or any other visit if they choose to withdraw before completing the study), they will be paid by money order for returning that device.

9. Consent Process:

- Written or verbal informed consent will be obtained from each subject at entry into the study. Written informed consent is obtained by the following process:
 - *Subject reviews the study consent form.*
 - *MPIs or research delegates speak with the subject to review the consent, confirm subject's understanding, and answer any questions.*

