Symptom Perception, Behavior, and Outcomes in Older Asthmatics

PI: [name] [name]

NCT03646669

Document Date: Jan 18, 2022

Pilot Test Protocol (Aim 4): Pilot test an intervention to correct under-perception of asthma symptoms in older adults.

Aim 4: Data Analysis: We will compare the baseline characteristics of patients randomized to the intervention vs. control arm using a t-test or chi-square test, as appropriate. Post intervention percent of symptom underperception among groups will be compared using a t-test or Wilcoxon test. In exploratory analyses, we will compare illness (IPQ scores) and medication (BMQ scores) beliefs, adherence (electronic measures, MARS scores), and other SMB (e.g., trigger avoidance) in the PEF intervention vs. control arm. We will also conduct secondary multiple regression analyses adjusting for potential differences in baseline characteristics (including 12-month underperception scores). Power for Aim 4: Based on a sample of 80 participants, the study will have >90% power to identify a clinically meaningful difference of 5 units in symptom perception.

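### The main Aim 4 comparison is an unadjusted two-sample test with no stated way to use both pilot follow-ups; one model with the 12-month score would be more precise

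*Protocol*

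**What the plan says.** The pilot's visit schedule appears in the Protocol's payment section (section 8). A first pilot interview takes place at 12.5 months, and a payment is then made "for each of the follow-up interviews (14 months and 15 months". Participants are also paid for returning the medication monitor and "the electronic peak flow meter after each pilot interview". Section 2 of the Protocol describes symptom perception as self-estimated against measured peak flow, so the meter is the likely source of the perception score, although no passage states that link for the pilot.

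The SAP (Aim 4: Data Analysis) gives the main comparison in one sentence: "Post intervention percent of symptom underperception among groups will be compared using a t-test or Wilcoxon test". It names no visit, no window and no rule for combining visits. The 12-month score enters only through "secondary multiple regression analyses adjusting for potential differences in baseline characteristics (including 12-month underperception scores". The power statement reads: "Based on a sample of 80 participants", "the study will have >90% power to identify a clinically meaningful difference of 5 units in symptom perception".

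**The concern.** A t-test or Wilcoxon test takes one number per participant. With follow-ups at 14 and 15 months and no combining rule, the analyst could use the first, the second, each in its own test, or a pool of both. Using one leaves information unused. Testing each separately gives two looks at one outcome. Leaving the choice open allows it to be made after the data are seen.

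The 12-month score raises a related point. It is collected before the pilot and is likely to predict the post-intervention score, yet the main test ignores it. In a pilot of 80 people, both choices affect how wide the confidence interval for the arm difference will be.

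**Working it through.** **1. The plan's own power figure.** From the SAP: 80 participants, a difference of 5 units, power above 90%. Not stated, so assumed: 1:1 allocation (40 per arm), two-sided 0.05, no dropout. The SD is not stated either, so the figure cannot be reproduced; it can only be solved backwards.

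- Normal approximation: SD = 5 / [(1.960 + 1.282) × √(2/40)] = 6.90. The noncentral t gives 6.81.
- So the claim of more than 90% holds only if the SD is below about 6.8 units. By t-test, power is 78.8% at SD 8 and 59.8% at SD 10.

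**2. How many pilot device periods there are.** From the Protocol, section 8: baseline 50 + 20, two follow-ups 2 × 40 + 2 × 20, pilot interviews 20 + 2 × 30, total $270. Two pilot device returns at $20 give $310, which is the stated maximum; three give $330. This favours two periods but does not settle it, because the same section speaks of a return after each of three pilot interviews and allows for a device issued at 15 months.

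**3. Variance gain from a second score.** Let r be the correlation between the two follow-up scores and b the correlation of each with the 12-month score (all assumed), with equal variance at both visits.

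- Unadjusted, the variance of the mean of two scores relative to one is (1 + r)/2. For r = 0.5, 0.6, 0.7, 0.8 and 0.9 this is 0.75, 0.80, 0.85, 0.90 and 0.95: cuts of 25%, 20%, 15%, 10% and 5%.
- Adjusted for the 12-month score, the ratio is [(1 + r)/2 − b²] / (1 − b²):
  - b = 0.5, r = 0.5: 0.50/0.75 = 0.667 (cut 33%)
  - b = 0.5, r = 0.8: 0.65/0.75 = 0.867 (cut 13%)
  - b = 0.6, r = 0.5: 0.39/0.64 = 0.609 (cut 39%)
  - b = 0.6, r = 0.8: 0.54/0.64 = 0.844 (cut 16%)

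The 39% corner has the 12-month score correlating more strongly with each follow-up than the two follow-ups do with each other, so it is the optimistic end.

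**4. Gain from the 12-month score alone.** With one follow-up score, adjustment multiplies the variance by 1 − b²: 0.75 at b = 0.5 and 0.64 at b = 0.6, cuts of 25% and 36%. This gain does not depend on how many follow-up scores exist.

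**5. Effect on power, unadjusted t-test, 5-unit effect at both visits, 40 per arm.**

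| SD | one score | two, r = 0.5 | two, r = 0.6 | two, r = 0.8 |
|---|---|---|---|---|
| 6.81 | 90.0% | 96.3% | 95.2% | 92.7% |
| 8 | 78.8% | 89.0% | 87.0% | 82.9% |
| 10 | 59.8% | 72.2% | 69.5% | 64.4% |

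**6. The downside.** If the effect is present at one visit only, the average halves it while the standard error shrinks only to √[(1 + r)/2]. At r = 0.6 the signal-to-noise ratio becomes 0.5/0.894 = 0.56 of what testing that one visit would give.

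**The case against.** A reader might infer that half of the post-intervention data is thrown away. The documents do not support that, for three reasons.

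- The outcome is a percent, already a summary over many readings. One percent per person can be formed from all post-intervention readings and put into a t-test. One value per person does not mean one visit. If that pooling is what is meant, most of the gain from a second score is already taken.
- The number of device periods is unclear, as the payment totals show, and no passage says which readings feed the score or when the intervention ends. If part of the first period falls within the intervention, averaging it in would not be a post-intervention measure.
- Half of the readings is not half of the precision: the unadjusted gain is 10% to 25% of variance, and 5% at a correlation of 0.9.

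It can also be said that averaging over visits answers a different question from the effect at one chosen time, and that a simple test is adequate for a pilot.

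The first three points stand, and they limit the concern to a conditional loss. They do not remove it: if pooling is intended, the SAP still has to say so. The fourth is a fair reason to report visit-specific differences, not a reason to leave the time point open. None of these points touches the fact that the main test leaves out the 12-month score.

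**Conclusion.** The point holds in a limited form. The main Aim 4 comparison is unadjusted, uses the 12-month score only in a secondary analysis, and states no method for using both follow-ups. If one follow-up alone is analysed, a second score would have cut the variance by 10% to 25% unadjusted, or by 13% to 39% after baseline adjustment. These ranges rest on assumed correlations (0.5 to 0.8 between visits, 0.5 to 0.6 with the 12-month score). The power figures further assume 40 per arm, two-sided 0.05, no dropout and the same effect at both visits.

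This is an improvement to the method, not an error that invalidates the pilot. The missing SD is the larger gap in the power statement; because it is missing, nobody can tell whether the pilot has precision to spare.

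**What to change.** Replace the main comparison in the SAP with wording such as: *The Aim 4 arm difference in percent underperception is estimated from one repeated-measures model with arm, visit, arm-by-visit and the 12-month score, as the average over the follow-up scores collected after the intervention ends. The visit-specific differences are reported beside it. If only one such score exists, ANCOVA on the 12-month score is used.*

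The SAP should also say when the intervention ends, which device periods yield a perception score, and what SD and alpha lie behind the power statement. The t-test or Wilcoxon test can stay as a supporting analysis.

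The cost is SAP wording and a little more analysis work, with no new visit or measurement. A participant with only one of the two scores still contributes. The price is dilution of an effect present at one visit only, which the visit-specific estimates would show. The SAP is dated January 18, 2022, after the March 31, 2021 end date in the Protocol's Study Timelines, so if the arms have already been compared, the new model should be labelled as chosen afterwards.

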Symptom Perception, Behavior, and Outcomes in Older Asthmatics

PI: [name] [name]

NCT03646669

Document Date: Jan 18, 2022

Pilot Test Protocol (Aim 4): Pilot test an intervention to correct under-perception of asthma symptoms in older adults.

Aim 4: Data Analysis: We will compare the baseline characteristics of patients randomized to the intervention vs. control arm using a t-test or chi-square test, as appropriate. Post intervention percent of symptom underperception among groups will be compared using a t-test or Wilcoxon test. In exploratory analyses, we will compare illness (IPQ scores) and medication (BMQ scores) beliefs, adherence (electronic measures, MARS scores), and other SMB (e.g., trigger avoidance) in the PEF intervention vs. control arm. We will also conduct secondary multiple regression analyses adjusting for potential differences in baseline characteristics (including 12-month underperception scores). Power for Aim 4: Based on a sample of 80 participants, the study will have >90% power to identify a clinically meaningful difference of 5 units in symptom perception.

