2. Resources Available to Conduct the Human Research: (the aim here is to assess if the research is likely to be successful and thus justify the efforts and risks taken by the subjects):

- We demonstrated the feasibility and validity of the proposed symptom perception methodology and clinical accuracy grid by showing that asthma symptom perception was associated with asthma morbidity across a 1-year follow-up. 15 Estimates of PEF as a measure of asthma symptom perception is more accurate than verbal descriptors (e.g.,

	Protocol Name:	Symptom perception, behavior, and outcomes in older asthmatics
	Principal Investigator:	[name]
	Primary Contact Name/Contact Info:	[name]
	Date Revised:	1/7/2021
	Study Number:	15-0667

difficulty with breathing) to communicate dyspnea when compared to actual PEF values.¹²³ The PEF self-estimate provides a common language that minimizes cultural differences in descriptors of dyspnea, which have been shown to vary by ethnicity.^{124,125} We found that there are no ethnic differences among Puerto Rican, African-American, and Afro-Caribbean children with asthma on symptom perception accuracy using the proposed methodology or in response to our PEF prediction with feedback intervention.¹⁴ We will recruit participants from general medicine and pulmonary outpatient clinics in the Mount Sinai Health System, at Jacobi Medical Center, and Montefiore Medical Center.

3. Study Design:

a) Recruitment Methods (see PPHS policy):

- Potentially eligible participants will be identified through monthly queries of the patient registration systems. The RAs will obtain permission from physicians to contact these patients. Emergency Department (ED) Recruitment: ED recruitment will increase enrollment of individuals who may use the ED as their usual source of care. RAs will query the ED's electronic registration system and will monitor the asthma treatment areas to identify potentially eligible patients. Once a potential participant is identified, the RAs will obtain permission from the ED physician and follow the steps described above. Please note that subjects will not require consent from a Primary Care Provider separate from their ED provider in order to participate in the study.
- We will recruit and introduce the study to participants using the following steps:

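### A possible low-cost precision gain, not an error: the leading Aim 4 comparison ignores the 12-month underperception score, which the plan uses only in a secondary regression

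*SAP*

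**What the plan says.** The Aim 4 analysis paragraph of the SAP gives the between-arm comparison first: "Post intervention percent of symptom underperception among groups will be compared using a t-test or Wilcoxon test". It names no covariate. Beliefs, adherence and other self-management outcomes are called exploratory. The paragraph then adds "secondary multiple regression analyses adjusting for potential differences in baseline characteristics (including 12-month underperception scores"). No other covariates are listed, and there is no rule for a missing 12-month score.

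The SAP never uses the word primary. That the unadjusted test leads is inferred from its position and from the labels on the other outcome analyses.

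The power statement is that, with 80 participants, "the study will have >90% power to identify a clinically meaningful difference of 5 units in symptom perception". It gives no SD, alpha, allocation ratio or correlation.

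On timing, Protocol section 8 (Payments/Reimbursements) places a follow-up interview at 12 months, the first pilot interview at 12.5 months, and pilot follow-ups at 14 and 15 months. The SAP itself counts the 12-month score as a baseline characteristic.

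**The concern.** A participant's score before the intervention usually predicts the score after it. If it does so here, part of the spread in the outcome is already explained by a measurement the study plans to hold, and a test that ignores it reports a wider interval than necessary. In a pilot of 80 the arm difference and its uncertainty are the main output, so interval width is what is at stake. Chance imbalance in the 12-month score is part of that same variance and should not be counted as a second benefit.

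The planned secondary regression does not fully meet the point. It is ranked below the unadjusted test, and its covariate list is open. It also follows planned baseline significance tests, which leaves room to choose covariates from the imbalance that happens to be seen.

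A practical question is how complete the covariate will be. Section 8 pays participants "after they return the electronic monitoring device for the medication and the electronic peak flow meter after each follow up interview", and adds that "Study participants will be paid in cash/money order for returning their devices at the next visit unless otherwise requested". Protocol section 2 refers to "Estimates of PEF as a measure of asthma symptom perception". If the 12-month score depends on the returned meter, some scores could be late or absent. The documents do not say whether it does.

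**Working it through.** **Inputs from the documents:** N = 80, a difference of 5 units, power above 90%. **Assumed:** 40 per arm, two-sided 5%, no dropout, r = 0.3, 0.5 or 0.7.

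**1. The plan's own figure.** Power above 90% cannot be reproduced without an SD, but the SD it requires can be found. With a noncentral t on 78 df, 90% power needs a standardised difference of 0.734, so SD = 5/0.734 = 6.81. The claim holds only if the SD is no more than about 6.8. I use 6.8 for the interval widths.

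**2. Variance of the adjusted difference.** With one normal covariate, relative to the unadjusted difference in means:

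variance ratio = (1 − r²) × [1 + 1/(80 − 4)] = (1 − r²) × 1.0132

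The second factor is the cost of estimating the slope. Break-even is at r² = 1/77, that is r = 0.114.

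**3. Results.** Equivalent N is 80/ratio. The unadjusted standard error is 6.8 × √(2/40) = 1.5205, so the unadjusted half-width is 1.9908 × 1.5205 = 3.03. The adjusted half-width is 1.9913 × 1.5205 × √ratio. Power uses 77 df and the SD that gives exactly 90% unadjusted.

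| r | Variance ratio | Equivalent N | Power | CI half-width |
|---|---|---|---|---|
| Unadjusted | 1 | 80 | 90% | 3.03 |
| 0 | 1.013 | 79.0 | 89.6% | 3.05 |
| 0.3 | 0.922 | 86.8 | 92.2% | 2.91 |
| 0.5 | 0.760 | 105.3 | 96.1% | 2.64 |
| 0.7 | 0.517 | 154.8 | 99.5% | 2.18 |

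**4. If the SD is larger.** At an assumed SD of 10, unadjusted power is 59.8%. With adjustment it is 63.3%, 71.7% or 86.7% at r = 0.3, 0.5 or 0.7.

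**5. Robust standard errors.** In simulation (normal scores, SD 6.8, 20,000 trials per setting), HC2 intervals had mean half-widths of 2.90, 2.63 and 2.17 against 3.02 unadjusted, with coverage of 94.9% to 95.1%. With skewed and floor-limited percentages, coverage stayed at 94.5% to 95.5% and intervals were still 3% to 25% narrower.

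**6. Missing 12-month scores.** These were set missing at random and replaced by the overall observed mean, with HC2 errors. The unadjusted half-width was 3.02, and coverage was 94.7% to 95.2%.

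| Missing | r = 0.3 | r = 0.5 | r = 0.7 |
|---|---|---|---|
| 10% | 2.91 | 2.67 | 2.27 |
| 20% | 2.93 | 2.72 | 2.37 |

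All these figures are for the model with arm and one covariate. They do not describe the planned regression with further, unlisted covariates.

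**The case against.** The strongest reply is that the adjusted analysis is already planned, the unadjusted test is valid, and the SAP names no primary analysis, so the point only re-orders two analyses that would both be reported. It is true that nothing essential is missing. But the planned regression is labelled secondary and its covariates are open, so it does not do the work of one pre-specified leading estimate.

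The second reply is that the gain rests on a correlation nobody has documented. That stands in full. At r = 0.3 the half-width falls by only 0.12 units, against a 5-unit meaningful difference. The pilot targets underperception. If entry required a high 12-month score (pilot eligibility is not shown), the restricted range would lower r. For example, with normal scores and only the upper half enrolled, r of 0.3, 0.5 and 0.7 becomes about 0.19, 0.33 and 0.51, and the variance cuts shrink to about 2%, 10% and 25%. These are still gains, because each r is above the break-even of 0.11.

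Third, the SAP is dated Jan 18, 2022, after the March 31, 2021 end of the timeline in Protocol section 3(d), so changing the leading analysis could be post hoc. The documents do not say whether outcomes had been examined by arm. If they had, the change needs that label and adds less over the secondary regression.

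Fourth, the meter-return concern is inferred from payment wording, and measurement details may lie in text not available here. That is fair. The recommendation to lead with the adjusted estimate does not depend on it.

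**Conclusion.** The point holds as an improvement, and the plan contains no error here. Leading with an unadjusted test gives up precision whenever r exceeds about 0.11. With 40 per arm, the variance of the arm difference would fall by about 8% at r = 0.3, 24% at 0.5 and 48% at 0.7, against a worst-case loss of about 1.3% at r = 0. Confidence is high in the reading of the SAP and in the direction of the trade-off. The size of the gain is unknown, because r is not given. If power does exceed 90% as claimed, the benefit is mainly a narrower interval. If the SD is well above 6.8, power would improve materially too.

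**What to change.** Make the leading analysis a linear regression of post-intervention percent underperception, at one named visit (section 8 lists 14 and 15 months), on arm and the 12-month score.

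- Keep the 12-month score in the model whatever imbalance is seen, use only values recorded before randomisation, and select no covariates from baseline tests.
- Report the adjusted difference with a 95% CI from HC2 standard errors in all cases, so that no choice depends on the outcome's distribution.
- State one rule for missing 12-month scores, for example the overall mean of the observed scores, ignoring arm.
- Keep the t-test or Wilcoxon test as a sensitivity analysis.
- If outcomes had been examined by arm before the change, label it post hoc.

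The cost is a few lines of SAP text and one degree of freedom. No new data are needed.

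### Does the SAP need a written rule for which pilot visit and which randomised participants enter the Aim 4 comparison?

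*SAP*

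**What the plan says.** The SAP, under Aim 4: Data Analysis, gives one between-arm comparison of the outcome: "Post intervention percent of symptom underperception among groups will be compared using a t-test or Wilcoxon test". The sentence before it, on baseline characteristics, refers to "patients randomized to the intervention vs. control arm", which is the only place where randomisation is mentioned. Secondary regressions adjust for baseline differences, "including 12-month underperception scores". The power statement begins "Based on a sample of 80 participants" and claims more than 90% power for a difference of 5 units. It gives no SD, significance level, allocation ratio or allowance for losses.

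The protocol adds the visit structure. Section 8 (Payments/Reimbursements to Subjects) lists a first pilot interview at 12.5 months and follow-up interviews at 14 and 15 months. It also arranges device-return payments for participants "if they choose to withdraw before completing the study". Section 3(i) (Withdrawal of Subjects) lets participants leave at any time and lets the investigator, sponsor or institution end participation, for example when instructions are not followed. Section 3(g) (Data and Safety Monitoring Plan) has the DSMB review withdrawals and their reasons every six months. Neither document defines an analysis set, an outcome visit or a missing-data rule.

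**The concern.** A t-test or Wilcoxon test takes one value per participant, but the pilot has two follow-up visits (both read here as after the intervention). Someone seen at 14 but not 15 months could be included with the 14-month value, left out, or carried forward. Analysing by assigned arm does not settle which.

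Two things would be at stake. First, if the rule were picked once results were visible, the chance of a false-positive finding would rise above 5%, even with losses equal between arms. Second, if the 80 are those randomised, the power claim has no visible margin for dropout. Removal for not following instructions could also fall unevenly between arms, so a completers-only comparison might be biased as well as smaller.

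**Working it through.** **The power figure.** It cannot be reproduced, because the SAP gives no SD. Assume 40 per arm, two-sided alpha 0.05 and a difference of 5. The noncentrality is 5 / (SD × √(2/n)), with n per arm, and power comes from the noncentral t distribution with 2n − 2 degrees of freedom. The largest SD that gives 90% power at n = 40 is 6.81. Taking SD 6.8, close to that limit:

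- n = 40: 5 / (6.8 × 0.2236) = 3.288, power 90.1%
- 10% loss, 72 analysed, n = 36: 5 / (6.8 × 0.2357) = 3.120, power 86.8%
- 20% loss, 64 analysed, n = 32: 5 / (6.8 × 0.25) = 2.941, power 82.5%

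At SD 6.0 the same three cases give 95.7%, 93.7% and 90.7%. Whether losses take power below 90% therefore depends on an SD and a dropout rate that neither document gives.

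**The false-positive rate if the rule were chosen afterwards.** The inputs are assumed: 40 per arm, no true effect, normal 14- and 15-month scores with equal variance and correlation r, and 15-month values missing at random with the same probability in both arms. Four rules are tested by t-test: the 14-month value, 15-month completers, last available value, and mean of available values. Each rule alone gives about 5%. The percentage of null trials in which at least one rule in the set is significant is:

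| Rules open to choice | Missing at 15 months | r = 0.5 | r = 0.8 |
|---|---|---|---|
| All four | none | 9.8% | 8.0% |
| All four | 10% | 10.8% | 9.1% |
| All four | 20% | 11.1% | 9.4% |
| 14-month value or 15-month completers | none | 9.1% | 7.8% |
| 14-month value or 15-month completers | 10% | 9.1% | 8.1% |
| 14-month value or 15-month completers | 20% | 9.2% | 8.2% |

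With the visit fixed at 15 months, and only completers versus last available open, the rate is 6.5% to 7.0% over 10% to 20% missing.

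**What the split shows.** Most of the excess exists with no missing data at all, so it comes from the unnamed visit. The question of who is analysed when data are missing is worth about 1.5 to 2 percentage points (6.5 − 5 and 7.0 − 5). Even that is reached only if the better-looking result is always the one reported.

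**The text itself.** The main comparison is between groups, the preceding sentence defines the groups by randomised arm, and no per-protocol or treatment-received set appears anywhere. The ordinary reading is that participants with outcome data are compared by assigned arm.

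**The case for a change.** The strongest case for a change is that the omission is real and cheap to repair. Nothing in the supplied text names the visit or the analysis set. DSMB review of withdrawals is oversight, and adjustment for the 12-month score deals with baseline imbalance; neither is a rule for missing outcomes. Leaving only the visit open can take the false-positive rate to about 8% or more, even with balanced losses, and a few sentences would close the gap without new data.

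The description of the gap stands, and so does the arithmetic. What does not follow is that the plan is wrong. The inflation needs a choice made after looking at the results, and nothing in the documents suggests one. Each candidate rule is sound if used consistently, and the proposed repair writes one of them down without replacing a faulty method by a better one. The protocol provides for withdrawal but gives no rate, so the scale of missing data is unknown. The power loss appears at an SD chosen to sit at the edge of the claim, while the SAP claims more than 90%. The clause on ending participation is permissive and says nothing about how the analysis treats those removed.

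**Conclusion.** The SAP leaves out the outcome visit, the handling of participants with one visit, and whether 80 means randomised or analysed. The size is modest. Under the assumed inputs, the upper-limit false-positive rate is about 8% to 9% from the visit choice and 6.5% to 7% from the missing-data rule, against about 5% for any single rule. Power falls to 86.8% or 82.5% only if the SD is near 6.8, 80 is the number randomised and losses reach 10% or 20%; at SD 6.0 or below it stays above 90% with 20% loss. No bias, inflated error or lost power is shown for this trial.

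For an 80-person pilot with one simple by-arm comparison, this is detail that a competent analyst supplies in the ordinary way: analyse by assigned arm, say which visit was used, and report how many in each arm contributed data. No stated rule needs correcting, so the plan can stand. The conclusion rests on the natural reading of the SAP as a by-arm comparison and on the text supplied.
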